5.4. Screen Failures

Screen failures are defined as participants who consent to participate in the clinical study but are not subsequently randomly assigned to study intervention. A minimal set of screen failure information is required to ensure transparent reporting of screen failure participants to meet the CONSORT publishing requirements and to respond to queries from regulatory authorities. Minimal information includes demography, screen failure details, eligibility criteria, and any SAE.

Individuals who do not meet the criteria for participation in this study (screen failure) may be rescreened. All screening procedures must be repeated, and the participant assigned a new 8-digit SSID number.

6. STUDY INTERVENTION

Study intervention is defined as any investigational intervention(s), marketed product(s), placebo, medical device(s), or study procedure(s) intended to be administered to a study participant according to the study protocol.

For the purposes of this protocol, study intervention refers to PF-06882961 and matching placebo tablets.

6.1. Study Intervention(s) Administered

For this study, PF-06882961 and matching placebo tablets will be administered orally BID with food.

PF-06882961 and placebo tablets will be supplied to the site as packaged blister cards and labeled according to local regulatory requirements.

Intervention Name	PF-06882961	Placebo for PF-06882961
ARM Name	Active	Placebo
Type	Drug	Drug
Dose Formulation	Tablet	Tablet
Unit Dose Strengths	10 mg, 40 mg and 100 mg	Not applicable
Dosage Levels	10, 20, 40, 60, 80, 100, 120 mg BID	0 mg BID
Route of Administration	Oral	Oral
Sourcing	Provided centrally by the sponsor. Refer to the IP Manual.	Provided centrally by the sponsor. Refer to the IP Manual.
Packaging and Labeling	Study intervention will be provided in blister packs. Each blister pack will be labeled as required per country requirement. Blinded labels will be utilized for titration and stable dosing blister packs.	Study intervention will be provided in blister packs. Each blister pack will be labeled as required per country requirement. Blinded labels will be utilized for titration and stable dosing blister packs.

6.1.1. Administration

Participants will take 3 tablets of study intervention (PF-06882961 or matching placebo) in the morning with food and 3 tablets of study intervention in the evening with food, approximately 10-12 hours apart and at approximately the same time each day. Participants will take a total of 6 tablets of study intervention (PF-06882961 or matching placebo) daily. Participants will swallow the study intervention whole, and will not crush, chew, break, or dissolve the study intervention prior to swallowing. Downward titration or dosing is not permitted during the study; participants who do not tolerate the titration scheme and/or assigned dose may be required to discontinue dosing of study intervention.

The titration schemes to be used in this study and additional details regarding titration are provided in [Section 1.2, Table 3](#) and the IP Manual.

Table 3. Titration Scheme and Dosing Level

Target Dose (mg)	Study Week							
	1	2	3	4	5	6	7	8
Placebo	0 mg BID	0 mg BID	0 mg BID					
40 mg BID	10 mg BID	20 mg BID	40 mg BID	40 mg BID	40 mg BID	40 mg BID	40 mg BID	40 mg BID
80 mg BID	10 mg BID	20 mg BID	40 mg BID	60 mg BID	80 mg BID	80 mg BID	80 mg BID	80 mg BID
120 mg BID	10 mg BID	20 mg BID	40 mg BID	60 mg BID	80 mg BID	100 mg BID	120 mg BID	120 mg BID

6.1.1.1. Inpatient and outpatient visit days

Morning dosing at approximately 0800 hours and evening dosing at approximately 1800 hours will occur with meals at the site on admission and during inpatient days in V2 and V10, except discharge days. For discharge days and outpatient visit days, morning dosing at approximately 0800 hours will occur with meals at the site. Participants will be instructed to arrive at the site in the fasted state for each of the scheduled visits. For V3-V10, participants will be instructed to bring their study intervention supply and dosing diary with them, and to delay self-administration of study intervention on scheduled visit days until directed to dose during their visit. When participants dose at the site, they will self-administer the study intervention under supervision by site staff. The date and time of each dose administered at the site will be recorded in the site source documents, in the diary and in the CRF. Additionally, the date and time of the previous 2 doses of double-blinded study intervention prior to each of the pre-dose PK blood collections (ie, the 2 most recent doses prior to the visit as noted in the diary) will be entered in the CRF.

Administration of blinded study intervention for all dosing regimens will occur under the conditions described in [Section 5.3.1](#).

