Days Relative to Dosing on Day 1 ^b	-28 to -3	Day -2 to Day 1	2	8	15	22	29	36	43	50	Day 55 to Day 56	57	58	63 - 70 84 - 91	
FSH (females only)	x														
HIV, HepBsAg, HepBcAb, HCVAb, syphilis	x														
Pregnancy test (females only)	x		x	x	x	x	x	x	x	x		x	x		
PF-06882961 PK ⁱ		x		x		x		x	x	x		x	x		
CCI															c
Urine Sampling for:															
Urine drug test	x														
Urinalysis (and microscopy, as appropriate)	x			x		x		x	x	x		x	x		
On-site urine pregnancy test (females only) ^j			x	x	x	x	x	x	x	x		x	x		

- a. Contact may occur via telephone and must occur 28 to 35 days from administration of the final dose of study intervention.
- b. Allowable time window for V3-V10 is ± 1 .
- c. Review glucometer and glucose log only.
- d. Physical examination may be performed at non-specified visits if there are findings during the previous exam or new/open AEs, if appropriate and at investigator discretion.
- C** f. Includes blood pressure and pulse rate; vital signs at Follow up, and early termination visit (if appropriate) are single; Triplicate vital signs should be conducted at Screening, prior to AM dose at 0H and at approximately 4H after AM dose on Days 8, 15, 22, 29, 36, 43, and 50. On Day 57, triplicate vital signs collected at 0H only. When a meal or snack is scheduled at the same time as vital signs, vital signs must be obtained prior to the meal/snack (See [Appendix 9](#)).
- g. 12-lead ECG at Screening, Days 15 and 43, Follow up, and early termination visit (if appropriate) are single; Triplicate ECGs should be conducted prior to AM dose at 0H and at approximately 4H after AM dose on Day 29. On Day 57, triplicate ECGs collected at 0H only. When a meal or snack is scheduled at the same time as an ECG, the ECG must be performed prior to the meal/snack (See [Appendix 9](#)).
- h. During inpatient stays, both AM and PM dosing will occur on the study site, except discharge day (Day 2). On outpatient visit and discharge day, AM dosing will occur at the study site, if applicable.
- i. PK samples to be collected prior to AM dose and at 4H after AM dose on Days 15, 29, and 43. Day 2 sample to be collected at 24H after AM dose on Day 1. Day 50 sample to be collected at 24H after AM dose on Day 49. Day 57 sample to be collected at 24H and 36H after AM dose on Day 56. Day 58 sample to be collected at 48H after AM dose on Day 56.

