5.3.1. Meals and Dietary Restrictions

- Participants must abstain from all food and drink (except water) at least 8 hours prior to CCI [REDACTED] the collection of the first blood sample (eg, glucometer measurement, safety laboratory, PK CCI [REDACTED] assessment) at Screening, each inpatient study day, each outpatient visit, and the follow-up visit.
- Water may be consumed as desired (ad libitum).
- Noncaffeinated drinks (except grapefruit or grapefruit-related citrus fruit juices - see below) may be consumed with meals and the evening snack.
- Participants will not be allowed to eat or drink grapefruit or grapefruit-related citrus fruits (eg, Seville oranges, pomelos) from 7 days prior to the first dose of study intervention until collection of the final PK blood sample.

- Details on the meals provided to participants at Visit 2 through Visit 10, including the menu items, portion sizes and approximate calories with nutritional macronutrient (% carbohydrate, fat and protein) breakdown of the meal will be maintained in source documentation at the site. This information will not be collected in the CRF, however may be submitted to the Sponsor upon request.
- On scheduled visits to the site, ***in the morning***, from Visit 2 through Visit 10, participants should be instructed to arrive **without** having morning meal/breakfast or self-administration of study intervention. ***Note:*** Participants may take their morning dose of antihypertensive and/or lipid modifying medication per their usual routine, if applicable.
- At Visit 2 through Visit 10, inclusive, the morning meal will be consumed with the study intervention at the site.
- Participants will be counseled on appropriate dietary and exercise guidelines for T2DM at Visit 2 and asked to maintain these guidelines throughout participation in the study. Counseling on dietary guidelines should be in accordance with local medical standards of care for patients with T2DM. ***Note:*** Participation in formal weight loss programs is prohibited during participation in this study.

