5.3.1.2. During inpatient days (Days -1, 1, 56 and 57)

- The caloric intake/menu assigned to each participant will be based on the Harris Benedict formula (sedentary lifestyle; to be provided to the site prior to study start) using the participant's body weight measured at screening.
- On days with MMTT as listed in [Table 2](#) of the [SOA](#) (including evening snack prior to MMTT) **only**: participants will be encouraged to consume all provided food, including the liquid meal and all standard meals provided on these days. In addition, the approximate percentage of food consumed should be recorded in CRF.
- Participants will not be required to consume all provided food during standard meals on Day 1 and Day 57.
- When a meal or snack is scheduled at the same time as an ECG, the meal will be provided after the ECG is completed.
- Breakfast will be provided with dosing at approximately 0800 hours each day while inpatient:
 - A standard breakfast will be provided on Day 1 with dosing and Day 57 except when the MMTT is administered;
 - For the MMTT, the mixed meal will be provided as 500 mL of ENSURE® H and will be administered as listed in [Table 2](#) of the [SOA](#). The entire ENSURE® H meal is to be consumed within approximately 10 minutes. (See [Section 8.6.1](#)).
- Lunch will be provided approximately 4 hours after AM dosing (approximately 1200 hours). On days with MMTT, lunch will be provided after the 4-hour postdose blood collection samples for the MMTT have been completed.
- Dinner will be provided approximately 10 hours after AM dosing (approximately 1800 hours).
- An evening snack may be provided at approximately 2200 hours.
- Meals on days with MMTT, will be standardized such that the participants receive the same menus for all meals on these days:
 - Participants will be encouraged to consume their entire meals on Days -1 and 56;
 - If participants do not consume their entire meal on Day -1, they will be instructed to consume the same amount of food ($\pm 10\%$) on the other days with MMTT that they ate on Day -1. If a participant consumes approximately $<90\%$ or $>110\%$ of what s/he consumed on Day -1 based on visual inspection by the site staff, the approximate percentage consumed should be noted on the source document;

- The start time of all meals will be captured in the CRF on days with MMTT including the ENSURE® H mixed-meal provided for breakfast.

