5.3.1.3. Discharge days (Days 2 and 58)

- The caloric intake/menu assigned to each participant will be based on the Harris Benedict formula (sedentary lifestyle; to be provided to the site prior to study start) using the participant's body weight measured at screening.
- Participants will not be required to consume all provided food during standard meals.
- A standard breakfast will be provided with dosing at approximately 0800 hours each day.

5.3.1.4. Outpatient visit days (Screening, Days 8, 15, 22, 29, 36, 43, 50 and V11 of Follow up visit)

- The caloric intake/menu assigned to each participant will be based on the Harris Benedict formula (sedentary lifestyle; to be provided to the site prior to study start) using the participant's body weight measured at screening.
- Participants will not be required to consume all provided food during standard meals.
- When a meal or snack is scheduled at the same time as an ECG, the meal will be provided after the ECGs are completed.
- A standard breakfast will be provided with dosing at approximately the same time each day.
- Lunch will be provided approximately 4 hours after AM dosing (approximately 1200 hours) except on V11 of follow up visit.

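### Minor: Protocol 6.1.1.1, 5.3.1, 5.3.1.2 and 5.3.1.3, read literally, place doses on Days 57 and 58, while the PK sample times, Table 3 and the V12 window fit a last dose on Day 56.

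*Protocol*

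**What the plan says.** Passages that, read literally, place doses after Day 56:

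- Section 6.1.1.1 has the morning dose at about 0800 and the evening dose at about "1800 hours will occur with meals at the site on admission and during inpatient days in V2 and V10, except discharge days". The next sentence reads: "For discharge days and outpatient visit days, morning dosing at approximately 0800 hours will occur with meals at the site". The same section makes administration subject to the conditions in Section 5.3.1, so the meal text cannot be set aside as purely dietary.
- Section 5.3.1: "At Visit 2 through Visit 10, inclusive, the morning meal will be consumed with the study intervention at the site".
- Section 5.3.1.2 has a title beginning "During inpatient days (Days -1, 1, 56 and 57", and its parent bullet says "Breakfast will be provided with dosing at approximately 0800 hours each day while inpatient".
- Section 5.3.1.3 is headed for Days 2 and 58 and says "A standard breakfast will be provided with dosing at approximately 0800 hours each day".

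Passages that fit a last dose on Day 56:

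- Table 1 footnote i: "Day 57 sample to be collected at 24H and 36H after AM dose on Day 56". The Day 58 sample is set at 48 h after that same dose.
- Sections 4.2 and 4.3.1 and Table 3 give eight weeks of dosing. Section 6.4 counts compliance through Week 8.
- Table 1 footnotes f and g schedule Day 57 vital signs and ECGs at 0H only.
- V12 falls on Day 84-91 and, by Table 1 footnote a, must be 28 to 35 days after the final dose.

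Section 4.1 says that dosing is completed at V10. That does not settle the matter, because V10 spans Days 55 to 58.

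**The concern.** A site working from 6.1.1.1 and the meal sections would find instructions to dose on Day 57, morning and evening, and on the morning of Day 58. A site working from footnote i and Table 3 would find none.

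The difference matters because the 24, 36 and 48 h samples supply the terminal phase for steady-state half-life, a named secondary parameter (Protocol Table 5, SAP Table 3). Doses taken between those samples would remove the decline that the half-life is estimated from. Day 56 alone is a poor substitute: the last time column in Table 2 is 14 h, only 4 h after the evening dose at 10 h, and the Tmax range in Section 2.2.2.2 is 3 to 6 h.

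**Working it through.** **1. The plan's own day counts.** Eight weeks end on Day 8 x 7 = 56. The V12 interval is the V12 day minus the last-dose day:

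| Last dose | V12 on Day 84 | V12 on Day 91 |
|---|---|---|
| Day 56 | 28 days | 35 days |
| Day 57 | 27 days | 34 days |
| Day 58 | 26 days | 33 days |

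Only Day 56 reproduces the stated 28 to 35 days exactly.

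**2. Hours from the latest dose to each late sample.** Time runs from the Day 56 morning dose, with the evening dose at 10 h. A sample due at the same time as a dose is taken first (Appendix 9).

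| Sample | No dose on Day 57 | Doses at 24 and 34 h on Day 57 |
|---|---|---|
| 24 h | 24 - 10 = 14 | 24 - 10 = 14 |
| 36 h | 36 - 10 = 26 | 36 - 34 = 2 |
| 48 h | 48 - 10 = 38 | 48 - 34 = 14 |

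**3. Effect on the slope.** For a straight line fitted to ln C at 24, 36 and 48 h, the deviations from the mean time are -12, 0 and +12. So

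slope = (12 ln C48 - 12 ln C24) / (144 + 144) = (ln C48 - ln C24) / 24.

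At steady state, repeating the Day 56 doses on Day 57 makes C48 = C24. The slope is then 0, and ln(2)/k_el has no value. This step needs only steady state and identical dosing on the two days.

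**4. Illustrative model.** This assumes one compartment with first-order absorption, at steady state, with doses at 0 and 10 h. The inputs come from Section 2.2.2.2: Tmax 3, 4 and 6 h (range 3-6 h) crossed with half-life 4.681, 6.4 and 8.090 h (range 4.681-8.090 h; 6.4 h is a mid-range value). The absorption rate is solved from Tmax.

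| Nine scenarios | C36/C24 | C48/C24 | Fitted half-life |
|---|---|---|---|
| No dose on Day 57 | 0.17-0.37 | 0.03-0.13 | 1.00-1.18 times true |
| Morning and evening doses on Day 57 | 1.65-4.13 | 1.00 | not calculable (slope 0) |

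Example without a Day 57 dose, Tmax 3 h and half-life 4.681 h: C48/C24 = 0.029, slope = ln(0.029)/24 = -0.1475 per hour, and half-life = 0.693/0.1475 = 4.70 h (4.68 h before rounding).

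**5. Falling back on Day 56.** In the model the evening peak comes at 12.4-14.0 h. At most two declining points then precede a Day 57 dose: 14 h, if drawn, and 24 h. The readable PK marks in Table 2 reach 12 h, though its cells may be shifted. A two-point estimate from 14 and 24 h gives 1.04-2.17 times the true half-life.

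**6. How many.** Three active arms of about 9 give 3 x 9 = about 27 participants at most.

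**The case against.** The strongest reply is that the first group of passages is loose, generic wording and not a dosing calendar. Much of this stands.

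- Section 5.3.1.4 attaches dosing to breakfast on a list of days that includes Screening and V11, when no study drug can be due. Read literally, 6.1.1.1 also covers Days -2 and -1, before randomization.
- The sub-bullet in 5.3.1.2 can be read as attaching dosing to Day 1 only, with Day 57 named for breakfast alone.
- Table 3 assigns no dose level after Week 8.
- In the copy reviewed, the marks in the Table 1 on-site administration row and the content of Figure 1 are unreadable. They may show the intended days.

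A reader might also cite Table 1 footnote h, "During inpatient stays, both AM and PM dosing will occur on the study site, except discharge day (Day 2"), as further evidence for dosing on Days 57 and 58. It should not be relied on. Naming only Day 2 may equally mean that no dose was foreseen on Day 58, and its next sentence limits discharge-day dosing to where applicable.

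A reader might infer that V12 would come too early. Footnote a ties the contact to the actual final dose, so Days 85-91 (last dose Day 57) or 86-91 (last dose Day 58) would still meet both windows.

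What remains is the conflict in the text. Table 2 removes Days -2 and -1 by starting administration on Day 1, but no readable sentence exempts Days 57 and 58 from 6.1.1.1 or 5.3.1.3. A clear Table 1 row would show the intent and still leave those sentences in place.

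**Conclusion.** This is a minor inconsistency, but the text is wrong as written. The documents do not support the stronger reading that the protocol plainly orders dosing on Days 57 and 58: most of its day counts fit Day 56, and the opposing passages are probably generic.

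The harm is conditional on a site giving the morning and evening doses of 6.1.1.1 on Day 57. Steady-state half-life would then probably be missing for those participants. The zero slope rests on steady state and repeated dosing; the ratios rest on the assumed one-compartment model. How likely a site is to act this way cannot be judged from the documents.

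A reader might also infer that a wrong half-life would be reported. That is unlikely. Only points judged terminal enter the regression, SAP 5.3.3 keeps known biased estimates out of the summaries, and site dose times go into the CRF. The loss would be missing values. AUC24 and Cmax are defined over 0-24 h, before any Day 57 dose, and the primary safety endpoint is unaffected. A Day 58 dose with breakfast would follow the 48 h sample and would only move the final-dose date.

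**What to change.** Reconcile Sections 5.3.1, 5.3.1.2, 5.3.1.3 and 6.1.1.1 with Table 1 footnotes h and i, Table 3 and the Table 1 administration row, in one statement on whether study intervention is taken on Days 57 and 58. This review does not say which reading is right. The cost is one protocol clarification, with no new data or visits and no change to the SAP.

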6.1.1.2. Non-visit days

Dosing and administration instructions along with a dosing diary, will be provided to participants to support at home dosing of study intervention. When participants self-administer the study intervention at home, they will record each dose in the diary.

Participants will be instructed to self-administer their study intervention according to administration instructions provided to the participant.

Participants should be instructed that if they forget to take their morning dose at their usual time, they should take the missed dose as soon as possible (with food) on the day it was missed, however, there must be at least an 8-hour interval between the missed dose and the next dose. If a dose is missed and the interval to the next dose is less than 8 hours, the missed dose should not be administered.

6.2. Preparation/Handling/Storage/Accountability

1. The investigator or designee must confirm appropriate temperature conditions have been maintained during transit for all study interventions received and any discrepancies are reported and resolved before use of the study intervention.
2. Only participants enrolled in the study may receive study intervention and only authorized site staff may supply or administer study intervention. All study interventions must be stored in a secure, environmentally controlled, and monitored (manual or automated recording) area in accordance with the labeled storage conditions with access limited to the investigator and authorized site staff. At a minimum, daily minimum and maximum temperatures for all site storage locations must be documented and available upon request. Data for nonworking days must indicate the minimum and maximum temperatures since previously documented for all site storage locations upon return to business.
3. Any excursions from the study intervention label storage conditions should be reported to Pfizer upon discovery along with any actions taken. The site should actively pursue options for returning the study intervention to the storage conditions described in the labeling, as soon as possible. Once an excursion is identified, the study intervention must be quarantined and not used until Pfizer provides permission to use the study intervention. Specific details regarding the definition of an excursion and information the site should report for each excursion will be provided to the site in the IP Manual.
4. Any storage conditions stated in the SRSD will be superseded by the storage conditions stated on the label.
5. Study interventions should be stored in their original containers.
6. Site staff will instruct participants on the proper storage requirements for take-home study intervention.
7. The head of the medical institution (where applicable) or study intervention administrator is responsible for study intervention accountability, reconciliation, and record maintenance (ie, receipt, reconciliation, and final disposition records), such as the IPAL or sponsor-approved equivalent. All study interventions will be accounted for using a study intervention accountability form/record. All study intervention that is taken home by the participant, both used and unused, must be returned to the investigator by the participant. Returned study intervention must not be redispensed to the participants.
8. Further guidance and information for the final disposition of unused study interventions are provided in the IP Manual. All destruction must be adequately documented. If destruction is authorized to take place at the investigator site, the investigator must ensure that the materials are destroyed in compliance with applicable environmental regulations, institutional policy, and any special instructions provided by Pfizer.

Upon identification of a product complaint, notify the sponsor within 1 business day of discovery as described in the IP Manual.

